8.10 Subject's Satisfaction Questionnaire

Subject's satisfaction questionnaire (yes/no questions) will be conducted by the subjects at screening and on study visits Day 28, Day 56 and Day 84.

Subjects will be asked the following questions and will score their satisfaction based on the grades below:

How satisfied are you currently with the appearance of your chin, neck and jawline area?

Score	Grade
0	Extremely Satisfied
1	Satisfied
2	Somewhat satisfied
3	Neither Satisfied nor Dissatisfied
4	Somewhat Dissatisfied
5	Dissatisfied
6	Extremely Dissatisfied

How happy are you with the appearance of your neck as it relates to your chin fat?

Score	Grade
0	Extremely Satisfied
1	Satisfied

2	Somewhat satisfied
3	Neither Satisfied nor Dissatisfied
4	Somewhat Dissatisfied
5	Dissatisfied
6	Extremely Dissatisfied

How satisfied are you with the result of your treatment*?

Score	Grade
0	Very satisfied
1	Satisfied
2	Somewhat satisfied
3	Somewhat dissatisfied
4	Dissatisfied
5	Very dissatisfied

How likely would you be to recommend this procedure to friends and family*?

Score	Grade
0	Extremely likely
1	Very likely
2	Somewhat likely
3	A little likely
4	Not at all likely

8.11 Biochemistry

Blood samples for the laboratory evaluation of biochemistry parameters will be collected at screening and at study visits Day 2, Day 7, 28 and Day 84.

If there are clinically significant alerts obtained on Day 7, an unscheduled visit will be added for additional blood sampling.

Complete blood cell count (CBC) will include a standard red blood cell (RBC), white blood cell (WBC) with differential, hemoglobin, hematocrit, platelets. A comprehensive metabolic panel will include serum alkaline phosphatase (ALP), alanine aminotransferase (ALT), aspartate aminotransferase (AST), glucose, calcium, globulin (calculated), phosphorus, chloride, sodium, potassium, blood urea nitrogen (BUN)/creatinine ratio (calculated), creatinine with GFR estimated, total bilirubin, albumin, albumin/globulin ratio (calculated), total protein, amylase, bicarbonate/carbon dioxide (CO₂), uric acid, gamma-glutamyl transferase (GGT), and lactate dehydrogenase (LDH).

Biochemistry parameters will be collected for safety assessments.

8.12 Vital Signs

Vital signs (systolic and diastolic sitting position blood pressure, pulse rate, respiratory rate, and body oral temperature) will be obtained at screening, baseline (pre and post dose) and at study visits Day 2, Day 4, Day 7, Day 14, Day 21, Day 28, Day 56 and Day 84.

Vital signs will be collected for safety assessments.

8.13 ECG

ECG tests will be performed at screening and at study visits Day 7 and Day 84. ECG will be performed in triplicates.

ECGs will be collected for safety assessments.

8.14 Visual Analog Scale (VAS)

Pain will be assessed as part of the AEs using Visual Analog Scale (VAS). A scale between 0 to 10 will describe the pain level, where 0 represents no pain and 10 score is intolerable pain. A score of 1-3 is categorized as mild, 4-6 is moderate and 7-10 is severe. VAS will be assessed on Day 1 (after injection), Day 2, Day 4, Day 7, Day 14, Day 21, Day 28, Day 56 and Day 84.

8.15 Adverse Events and Serious Adverse Events

8.15.1 Collection of Adverse Events Data

An AE is any unfavorable and unintended sign, symptom, or disease temporally associated with the use of an investigational (medicinal) product (IP) or other protocol-imposed intervention, regardless of attribution. An AE may include intercurrent illnesses or injuries that represent an exacerbation (increase in frequency, severity, or specificity) of pre-existing conditions (e.g., worsening of asthma). A laboratory abnormality will be reported on the “Adverse Event” case

report forms only if it is associated with clinical sequelae or requires therapeutic intervention. Whenever possible, it is preferable to record a diagnosis as the AE term rather than a series of symptoms relating to a diagnosis. AEs will be coded according to the Medical Dictionary for Regulatory Activities (MedDRA) and graded for severity. In case the AE severity is changed from one severity grade to the another the date of AE start and AE end of the specific AE severity should be recorded.

The reporting period for AEs starts after dosing of study drug and will end at final study visit. If an AE remains unresolved at discharge, the subject will be followed, at the Investigator’s discretion, until resolution of the event or until the subject is deemed “lost to follow-up”. SAEs must be followed until resolution by the PI, even if this extends beyond the study-reporting period. Resolution is defined as the return to baseline status or stabilization of the condition with the expectation that it will remain chronic.

The Investigator will assess AEs for severity, relationship to IP, and as to whether the event meets one or more of the definitions of an SAE. The assessments will be recorded on the source documents and AE CRF, using the categories defined below.

Causality Category	Description
Unrelated	A clinical event, including laboratory test abnormality, with a temporal relationship to drug administration which makes a causal relationship improbable, and in which other drugs, chemicals or underlying disease provide plausible explanations. For the purpose of this protocol, the term unlikely will be considered not related to study medication and an “Adverse Event”.
Related	A clinical event, including laboratory test abnormality, with a reasonable time sequence to administration of the drug, but which could also be explained by concurrent disease or other drugs or chemicals. Information on drug withdrawal may be lacking or unclear. For the purpose of this protocol, an event that has possible or probable relationship to study medication will be defined as a “Suspected Adverse Drug Reaction”.

In order to classify AEs and diseases, preferred terms will be assigned by the sponsor or its designee to the original terms entered on the CRF, using MedDRA.

AEs will be graded for severity according to the following definitions:

Table 5 Severity Assessment of Adverse Events

Common Term	Description
Mild	Mild; asymptomatic or mild symptoms; clinical or diagnostic observations only; intervention not indicated.
Moderate	Moderate; minimal, local or noninvasive intervention indicated; limiting age-appropriate instrumental Assisted Daily Living

Common Term	Description
	(ADL).
Severe	Severe or medically significant but not immediately life-threatening; hospitalization or prolongation of hospitalization indicated; disabling; limiting self-care ADL.
Life-Threatening	Life-threatening consequences; urgent intervention indicated.
Death	Death related to AE

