	
4. RZL-012 and Celecoxib and cetirizine (200 mg Celecoxib BID and 10 mg cetirizine BID on Days 1, 2, 3, 4, 5 and 6)
 
5. RZL-012 + sling/pressure garment (until Day 6)
 
In the first stage of the study, 5 subjects will be randomized into each of the treatment groups. Study outcomes will be assessed up to one week thereafter to determine the need to modify additional study treatments. Subsequently up to 10 additional subjects will be randomized into each of the treatment groups for the second stage of the study.
 
For each subject, the study will consist of a screening period, baseline period in which subjects will receive a single treatment session of RZL-012 and a follow-up period. RZL-012 will be administered during a single treatment session via multiple injections into the submental area under the chin. Subjects will thereafter be monitored for safety and efficacy for at least 84 days.
 
Each subject will be treated with the same dose of RZL-012 :
 
• RZL-012 (concentration of injected solution 50 mg/mL RZL-012) of 7.5 mg/0.15 mL/injection point that results in a total dose/volume of 240±30mg mg/4.8±0.6 mL RZL-012, 
Each subject will receive additional study treatments in accordance with the treatment group to which the subject is randomized.
 
Screening Period:
 
Subjects will undergo screening within 28 days prior to being treated with RZL-012. During the screening period subjects will be assessed for study eligibility by evaluation of subjects' SMF using S-CAT , C-CAT, biochemistry blood tests, MRI, 2D photography. ECG will also be conducted during the screening visit. Following completion of study procedures (including MRI), subjects will be randomized in order for the PI to administer subjects with the Rx prescription, if appropriate (i.e., Celecoxib / cetirizine).
 
Day 1/Baseline:
 
At Baseline visit, subjects will be given with their randomized medication if appropriate. Subjects will receive a single multi-injection treatment of RZL-012 on Day 1. AEs will be recorded. Subjects will be asked about their pain levels using VAS. Additional medications/treatments, will be given according to its instructions for use.
 
Day 1-Day 84 Follow-Up Period
 
Subjects will return to the site for study visits on Days 2, 4, 7, 14, 21, 28, 56 and 84 for efficacy and safety assessments.
 
For subjects having unresolved AEs on Day 84, an unscheduled visit will be set 6-8 weeks after Day 84 to verify the resolution of the AE. On that visit, follow up of using photographs C-CAT and S-CAT will also be conducted.
 
Subjects will be advised to continue their regular diet and physical activity during the study.
 
Safety assessments include vital signs, ECG, AEs severity assessment, and treatment area evaluation. Treatment area evaluations including, but not limited to evaluation of edema, bruising, dysphasia, dysphonia, erythema, dyspigmentation, induration, numbness, pain, paresthesia, pruritus, skin ulceration and necrosis, injury to the marginal mandibular nerve, vascular and nerve injury and tissue damage to nearby vulnerable anatomic structures. Specifically, degree of swelling severity will be assessed as a function of time and in each visit Subjects will be asked about their pain levels using VAS. Pain at injection site will not

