	
Subjects will be injected with RZL-012 perpendicularly (90°) to the skin. An ice pack will be placed on the injected area for pain relief immediately after injection. Subjects will remain seated in the injection position for an additional 10 minutes after dosing.
 
The injection pattern will be based on a submental area shaped grid in which the distance between rows and columns will be 1 cm, as seen in the figure below. The Investigator will choose 32±4 sequential points on the grid that will mark the injected area according to SMF fullness and convexity. The treatment area boundary: superiorly by a line 1 cm inferior to the mandibular margin, laterally by the sternocleidomastoid muscles, and inferiorly by the hyoid bone.
 

Safety Analysis
	
AEs will be collected and reviewed to evaluate the safety and tolerability of RZL-012. AE collection will begin after dosing and will end at on Day 84. For subjects having unresolved AEs on Day 84, an unscheduled visit will be set 6-8 weeks after Day 84 to verify the resolution of the AE.
 
Other safety measures will include vital sign measurements, laboratory parameters, ECG, and treatment area evaluation including, but not limited to evaluation of edema, bruising, dysphasia, dysphonia, erythema, dyspigmentation, induration, numbness, pain, paresthesia, , pruritus, skin ulceration and necrosis, injury to the marginal mandibular nerve, vascular and nerve injury and tissue damage to nearby vulnerable anatomic structures. Specifically, swelling severity will be assessed in each visit, subjects will be asked about their pain levels. Pain at injection site will not be recorded as an AE but the information regarding pain will be obtained from the VAS scores completed by the subject. AEs related to nerve injury will be AEs of special interest. Concomitant medications will be recorded.

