1.2. Scientific Background

RZL-012 is a cytolytic drug - it disrupts cell membrane integrity which results in necrotic cell death. RZL-012 demonstrated a cell killing effect on cultured adipocyte, fibroblasts and HepG2 cells with IC₅₀ values ranging between 20-100 µM. In vivo pig studies demonstrated liponecrosis at the injection site, followed by a transient inflammatory response and finally, a healing process in which fibrotic tissue replaces previous fat tissue. Necrosis of fat tissue at the injection site was seen as early as 24 hours after injection and was still evident 2 weeks later but completely cleared by 12 weeks post dosing. A macrophage-mediated inflammatory response was also prominent at 24 hours and 14 days after injection with only minimal signs of inflammation remaining by 12 weeks post dosing. Fibrosis showed a different pattern compared with liponecrosis and inflammation, starting at 14 days post dosing and becoming much more prominent at 12 weeks post dosing. In essence, RZL-012 enabled de-novo generation of fibrotic tissue to replace excess fat tissue at selected anatomical sites.

To date, Raziel has conducted several clinical studies under INDs to evaluate the safety and efficacy of RZL-012 for local fat reductions, including obesity (INDs 119941, 133324), lipomas of Dercum's Disease patients and SMF (IND 135762) and SMF and flank reduction (IND 154260). Across all clinical trials approximately 222 subjects have received single doses of RZL-012 ranging from 5 mg to 412 mg per subject.

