9.4 Safety

Safety data will be summarized by dose group and based on their initial dose level or treatment group (i.e., if a dose reduction occurs, they will be considered in their initial group). Descriptive statistics will be provided for actual values and change from baseline values for vital signs, blood parameters, ECG.

AE assessment and treatment area evaluation including, but not limited to evaluation of edema, pain, bruising, erythema, induration, numbness, paresthesia, tenderness, and pruritus. Pain in the injection site will be assessed by Visual Analog Scale (VAS) in each of the visits. Injection site pain will not be recorded as an AE.

The incidence and severity of AEs reported during the study and their relationship to study drug will be tabulated. AEs will be coded using MedDRA™ and will be presented by body system.

AEs related to nerve damage such as: paralysis, mandibular neuropathy, facial palsy will be AEs with special interest, i.e., the PI will write a detailed narrative on these specific AEs.

AE data will be listed individually and summarized by SOC and by PT within a system organ class.

Skin irritancy AEs related to the injection procedure will be evaluated for frequency, severity and duration by treatment group.

Laboratory tests and ECG results will be summarized in appropriate table.

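### Because resolution includes chronic stabilisation, an adverse event judged permanent by Day 84 could count as resolved, fall outside the later visit and be summarised like one that cleared

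*Combined protocol and SAP*

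**What the plan says.** Section 8.15.1 (Collection of Adverse Events Data) gives the follow-up rules and the definition in one paragraph. For ordinary AEs: "If an AE remains unresolved at discharge, the subject will be followed, at the Investigator’s discretion, until resolution of the event". For serious AEs: "SAEs must be followed until resolution by the PI, even if this extends beyond the study-reporting period". The definition comes next: "Resolution is defined as the return to baseline status or stabilization of the condition with the expectation that it will remain chronic".

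The synopsis (Section 1.1) states a Day 84 rule twice, under Study Design and under Safety Analysis: "For subjects having unresolved AEs on Day 84, an unscheduled visit will be set 6-8 weeks after Day 84". It does not say what makes an AE unresolved. Section 8.15.1 does not mention this visit.

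Section 9.4 (Safety) tabulates incidence, severity and relationship to study drug, and lists AE data individually. It plans one analysis that depends on when an event ends: "Skin irritancy AEs related to the injection procedure will be evaluated for frequency, severity and duration by treatment group". It also says that "AEs related to nerve damage such as: paralysis, mandibular neuropathy, facial palsy will be AEs with special interest", and requires a detailed narrative from the investigator for these events. Section 8.15.2 includes persistent or significant disability among the criteria for a serious AE.

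**The concern.** The definition joins two opposite outcomes under one word: the subject recovered, or the subject is left with a stable condition that is not expected to go away. The word then does work elsewhere. It closes follow-up in Section 8.15.1, it is the natural key to who is unresolved at Day 84 in the synopsis, and it is the only guide a site has to when an event ended.

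This trial is more exposed than most. Its primary objective (Section 3.1.1) compares add-on treatments on AEs caused by RZL-012, and its primary endpoint (Section 3.2.1) is the safety profile. Whether a local reaction clears or stays is part of what the arms are meant to be compared on. The synopsis names induration, numbness, dyspigmentation and nerve injury among the treatment-area evaluations, and the Study Rationale describes nodules, induration and edema as drug related. If permanence and recovery are not kept apart, an arm with lasting events may look like one whose events cleared.

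**Working it through.** The plan has no figure to reproduce. The check sets the definition beside each place that depends on it.

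1. **Scope of the definition.** It follows the sentence on serious AEs, but the same paragraph has already used the term for ordinary AEs, and nothing limits the definition to serious ones. No competing definition appears in the available text.

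2. **Day 84 trigger.** The visit window is 6 × 7 = 42 to 8 × 7 = 56 days after Day 84, so Day 84 + 42 = 126 to Day 84 + 56 = 140. Three cases follow if the Section 8.15.1 definition is applied to the synopsis:
   - AE back to baseline by Day 84: resolved, no visit.
   - AE still changing, or of uncertain course, on Day 84: unresolved, visit at about Days 126-140.
   - AE judged stable and expected to be chronic by Day 84: resolved by definition, no visit.

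   The third case is the problem. Even where the visit takes place, its stated purpose is unclear under this definition: "an unscheduled visit will be set 6-8 weeks after Day 84 to verify the resolution of the AE". A finding of permanence at that visit would also meet the definition.

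3. **AE outcome.** Section 8.15.1 asks the investigator to assess severity, relationship and seriousness. No outcome category is described, and Section 9.4 tabulates no outcome. Persistence is therefore visible only in listings and, for nerve injury, in narratives.

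4. **Duration.** Section 9.4 plans duration for skin irritancy AEs. The only end-date instruction in Section 8.15.1 concerns a change of severity grade. There is no rule for an event that stabilises without clearing. As an illustration, assume onset on Day 14 and an end date taken from the definition:
   - cleared on Day 84: 84 - 14 = 70 days;
   - judged permanent on Day 84: also 84 - 14 = 70 days;
   - the same permanent event treated as ongoing: censored at 70 days, or, if still present at the later visit, at 126 - 14 = 112 to 140 - 14 = 126 days.

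   The Day 14 onset is an assumption, and the documents do not say whether induration belongs to the skin irritancy group.

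5. **Size per subject.** Section 9.1 gives 15 subjects per arm. One subject is 1/15 = 6.7 percentage points of an arm's rate of persistent events. The plan does not compute that rate, so this is the weight of one subject, not a predicted bias.

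**The case against.** The strongest reply is that the definition is only a stopping point for follow-up. It comes straight after two sentences on how long to follow events, and the documents nowhere say that a stabilised AE is coded as resolved. That reading is fair and cannot be excluded. But the same paragraph and the synopsis both use the term to sort subjects, and nothing tells a site to use a different meaning for outcome or duration.

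Several stronger readings are tempting and are not supported:

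- A reader might infer that a permanent event is recorded as resolved and given an end date. No outcome coding or end-date rule for stabilised events is stated. The case report form and the section on serious AE reporting are not in the available text, so they cannot be judged.
- A reader might infer that permanent events always miss the later visit. They do so only if the investigator has already judged them stable and chronic by Day 84.
- A reader might infer that permanent nerve injury would be indistinguishable from recovery. The narrative requirement, the individual listings and the disability criterion for serious AEs make that unlikely. Nor is nerve injury named in the duration analysis.
- A reader might infer from the pig data that induration will be permanent. Section 2.0 (Scientific Background) describes fibrosis as "starting at 14 days post dosing and becoming much more prominent at 12 weeks post dosing", and 12 weeks is Day 84. But it presents this as healing tissue that is still changing, which argues against a judgement of stability at that time. The available text gives no human data on persistence.

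What remains is that the safeguards cover nerve injury only in part. A mild, lasting induration or dyspigmentation has no narrative requirement and would not ordinarily meet the disability criterion. Neither safeguard yields a count of persistent events by arm.

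**Conclusion.** The point holds in a limited form. The only definition of resolution treats chronic stabilisation like recovery, and no separate AE outcome is described. An AE judged stable and permanent by Day 84 could therefore count as resolved, fall outside the visit at about Days 126-140 and, if it is a skin irritancy AE, enter the duration summary with a finite length. No planned table would separate it from an event that cleared.

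This rests on two assumptions: that the Section 8.15.1 definition governs the word unresolved in the synopsis, and that the investigator makes the judgement of chronic stability by Day 84. The number of subjects affected cannot be estimated from the documents. The change is worth making because safety is the primary endpoint and each subject carries 6.7 percentage points of an arm's rate.

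**What to change.** - **Section 8.15.1:** for AE outcome and analysis, define resolved as return to baseline only. Record a separate outcome for events that are not resolved but have stabilised or left sequelae. Stabilisation may stay as a point at which follow-up closes, under its own label.
- **Section 9.4:** in the duration summary, treat stabilised events as ongoing and censor them at last contact. Report the number of unresolved or stabilised AEs by arm, with nerve-injury events shown separately.
- **Synopsis and Section 8.15.1:** reconcile what counts as unresolved at Day 84. The synopsis says a visit is set, while Section 8.15.1 leaves follow-up to the investigator's discretion and lets resolution include chronic stabilisation.

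The cost is one more category on the case report form, a few sentences of text, possibly a few more visits after Day 84 depending on how the passages are reconciled, and a less favourable picture of resolution.

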8.15.2 Serious Adverse Events

According to the ICH Guidelines for Good Clinical Practice (E6), an SAE is any untoward medical occurrence during the course of a clinical investigation that is characterized by one or more of the following:

- Results in death
- Is life-threatening
- Requires in-subject hospitalization or prolongation of existing hospitalization
- Results in persistent or significant disability/incapacity
- Is a congenital anomaly/birth defect
- Important medical events

Although not an SAE, exposure to study drug during pregnancy, even if no AE is reported in the mother, should be reported within 24 hours.

